#### 6.1.2. Sensitivity/Robustness Analyses

*A sensitivity analysis of the time to climb 4 stairs will be based on the velocity (defined as the reciprocal of time). This analysis will use the same longitudinal model, but subjects who can no longer complete the assessment or ambulate will be analyzed with a velocity of 0 instead of a missing time to climb 4 stairs at that time point. Thus the missing data will no longer be handled using maximum likelihood techniques under the missing at random assumption for subjects who can no longer complete the 4 stair climb. Transformation of the velocity data will be used to meet model assumptions, if the velocity data are not normally distributed based on plots of the residuals. Based on the number of subjects who cannot complete the function test at Week 49, a zero inflation model may also be explored for the velocity endpoint. The point at which the zero inflated model will be explored is if more than 15% of the subjects cannot complete the timed function test.*

*Additionally, a non-parametric sensitivity analysis of the time to climb 4 stairs data may be performed on the Week 49 data if there is a large number of subjects who can no longer ambulate or complete the functional assessment. The Wilcoxon rank sum test will be used to compare the distributions of the two populations. The proportion of subjects who can no longer complete the test will also be compared between the two treatment groups at the Week 49 time point along with a time to failure analysis comparing the active to placebo groups based on the time to loss of the ability to complete the test. These analyses will be performed if more than 10 total subjects cannot ambulate or complete the 4 stair climb functional assessment.*

*A completer analysis will also be conducted as a sensitivity analysis for the missing data handling under the mixed effects modeling. The completer analysis will only include subjects that completed assessments through Week 49 using the same longitudinal mixed effects model as the primary analysis. An additional sensitivity analysis of all subjects in the treated group who dose escalated to the maximum dose will also be performed. This analysis will compare data at Week 49 for all subjects that dose escalated to 40 mg/kg. Lastly, a sensitivity analysis for the longitudinal mixed effects model including the interaction term of*

baseline by visit may be explored to evaluate if the effect of the baseline measurement on the timed function test varies over time.

In addition, as described in [Section 6.1.1](#), PPAS will be used to assess the sensitivity of the primary efficacy analysis result using FAS.

A summary plot of the cumulative percent of patients with a percent change from baseline on 4SC time less than a given set of thresholds (from <0% to <100%) will also be produced by sequence at Week 49 and at Week 97.

## 6.2. Secondary Endpoints

*Secondary endpoints of change from baseline at Weeks 17, 33, and 49 in FVC, Northstar Ambulatory Assessment (including time to stand and 10 meter walk/run), ROM, PUL, 6MWD, myometry based strength assessments, and MRI muscle volume (including mean percent change in Whole Thigh Muscle Volume and in Whole Thigh Muscle Volume Index defined in [Section 3.3.2](#)) endpoints will be analyzed using the same longitudinal mixed model as described for the primary analysis. Transformation of the data will also be considered if model assumptions are not met. These analyses will be based on the FAS. Analyses using PPAS may be explored to assess the sensitivity of analysis results. The baseline stratification factor will be included in the model along with the other effects described in [Section 6.1.1](#). For the MRI endpoints of Whole Thigh Muscle Volume and Whole Thigh Muscle Volume Index, baseline age may be included as an additional covariate, if needed, to account for growth. If a high degree of collinearity is observed between the baseline value for other time function tests and the stratification factor, the baseline time for the functional test of interest will remain in the model. The same model estimates and graphical displays will be created for the secondary analyses as described in [Section 6.1.1](#).*

*Additionally, a sensitivity analysis based on velocity may also be performed as described for the primary analysis for other timed function tests.*

For the change from baseline to Week 97 in 4SC, 6MWD, FVC, NSAA, the subjects randomized to Sequence 1 will be compared against the historical control group (see [Section 6.2.1](#)) using the same statistical analysis methods as described earlier for the primary and secondary analyses.

In the pre-specified subset of subjects who have baseline 4SC <3.5 seconds,  $\geq 3.5$  seconds and  $\leq 8$  seconds, or >8 seconds, changes from baseline as compared to placebo on muscle strength by myometry, on MRI muscle volume, and on function tests including, 4SC, FVC, NSAA, PUL, 6MWD at Week 17, 33 and 49 will be analyzed using the same statistical methods as described earlier for the primary and secondary analyses.

For the MRI endpoints of mean percent change in Whole Thigh Muscle Volume and Whole Thigh Muscle Volume Index, a regression model will be performed to evaluate the predictive relationship of each of the MRI endpoints at earlier time point to the primary endpoint 4SC time at later time point. This is conducted by evaluating MRI endpoint at Week 17 as a predictor variable to 4SC time response at Week 17, 33, 49 and 97 respectively, by evaluating MRI endpoint at Week 33 as a predictor variable to 4SC time response at

Week 33, 49 and 97 respectively, and by evaluating MRI endpoint at Week 49 as a predictor variable to 4SC time response at Week 49 and 97 respectively, with a treatment-(or sequence as appropriate)-by-MRI endpoint interaction that may be included in the model to account for potential different relationship in treatments or sequences. This analysis will be repeated for the pre-specified subset of subjects who have baseline 4SC <3.5 seconds,  $\geq 3.5$  seconds and  $\leq 8$  seconds, or >8 seconds. Transformation of the data will be considered if model assumptions are not met. Covariates such as age and baseline values will be explored and included as appropriate.

### **6.2.1. Historical Control**

*In keeping with global guidance (eg, Food and Drug Administration’s Guidance from 2015: Duchenne Muscular Dystrophy and Related Dystrophinopathies: Developing Drugs for Treatment and European Medicinal Agency[EMA]/Committee for Medicinal Product for Human Use [CHMP] Guideline on the Clinical Investigation of Medicinal Products for the Treatment of Duchenne and Becker muscular dystrophy, 2016) and related advice received from regulators, the long-term effects on functional assessments following approximately 2-years of treatment with PF-06252616 will be characterized compared to a historical control. This historical control group will be established by filtering available natural history datasets (eg, CINRG dataset) to match covariates including but not limited to baseline 4SC time range, baseline age interval, and the baseline glucocorticosteroids requirements defined by the protocol.*

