Exposure from the first 12 subjects will be reviewed to confirm that the exposure in the pediatric population is consistent with model predictions from the healthy adult volunteer study. This will occur following at least one dose at the 5 mg/kg dose level and will occur again following at least one dose at 20 mg/kg dose level. Should there be any clinically relevant differences in exposure versus those predicted; a dose adjustment may be made as agreed with the E-DMC. This analysis will be performed by a group of unblinded Clinical Pharmacology scientists not directly involved in the day to day conduct of the study. It is planned that recruitment would continue during this evaluation period.

The study will remain double-blinded until the time of the primary analysis for safety and efficacy (after the last enrolled subject completes 49 weeks). At that time, a limited number of study team members will be unblinded to the treatment assignments. The sites (with the exception of unblinded site personnel eg, the pharmacist) and the subjects will remain blinded to their study treatment through the conclusion of the study.

The following is a schematic of the study design.

Note: Sequence 1, Period 2 demonstrates subjects continuing on the maximum tolerated dose from Period 1 for each individual subject, as per the dose adjustment criteria (Table 2). SCRN=Screening, PBO=Placebo, W=Weeks

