2	
In Section 2.1.2, two secondary objectives and endpoints have been added.
 
S6: To characterize the long-term effects following approximately 2-years of treatment with PF-06252616 on functional assessments compared to historical control.
 
S7: To characterize the effects of PF-06252616 on muscle strength and functional assessments compared to placebo in subset of subjects who may demonstrate a rapid disease decline and with relatively low variability over a one-year period (see Section 6.4 for the
	
 
The first objective was added to further describe how data from Sequence group 1 (subjects who will receive PF-06252616 in both Period 1 and 2 for approximately 2 years) will be evaluated for long-term efficacy. Upon review of additional Duchenne muscular dystrophy (DMD) natural history data of the 4 stair climb (4SC) which recently became available from 4 separate studies (The Cooperative International Neuromuscular Research Group [CINRG], University of Cincinnati [UofCCNT], University of Florida [UofFLA] and Leuven), the mean change in 4SC observed over 1 year was less (ranging from 0.9 to 1.99 seconds) in DMD patients who are 6 to <10 years old with a baseline 4SC of 2.5 to 12 seconds than originally estimated (~2.9 seconds) from the data available at the time when the protocol was first written. In addition, the natural history data showed that the 4SC time change over two years is approximately 4.3 seconds on average (in DMD patients who are 6 to <10 years old with a baseline 4SC of 2.5 to 12 seconds).
 

090177e1909dd632\Approved\Approved On: 25-Mar-2019 05:54 (GMT)

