## 6. ANALYSES AND SUMMARIES

### 6.1. Primary Endpoint

#### 6.1.1. Primary Analysis

The primary endpoint, change from baseline in 4 stair climb, will be analyzed based on the FAS using the mixed effects model outlined in [Section 5.2](#). For primary efficacy analysis, besides FAS, PPAS will be used to assess the sensitivity of the analysis results. These analyses will be performed based on the data for all subjects through 49 weeks. Subjects in sequence 1 and 2 will be combined for analysis purposes and compared to the placebo subjects in sequence 3. Covariates for this analysis include the time to climb 4 stairs at baseline, treatment, visit and treatment by visit interaction. Model estimates and change from placebo estimates, 95% two-sided confidence intervals, and p-values will be displayed for study interpretation purposes. Model estimates with confidence intervals will also be displayed graphically. Graphical summaries of the raw data, including boxplots, will be created to highlight outliers and other influential observations.

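### The Week 97 historical-control comparison selects controls by range filters from open sources and does not adjust for age or steroid regimen, so it can be confounded

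*SAP*

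**What the plan says.** SAP Section 6.2.1 describes the comparator as "established by filtering available natural history datasets (eg, CINRG dataset) to match covariates including but not limited to baseline 4SC time range", and continues with "baseline age interval, and the baseline glucocorticosteroids requirements defined by the protocol". No subject-level matching, weighting, balance check, control-group size, pooling rule or lock date follows. Protocol Section 9.2.2.1 adds no method.

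SAP Section 6.2 compares Sequence 1 with this group on change to Week 97 in 4SC, 6MWD, FVC and NSAA, "using the same statistical analysis methods as described earlier for the primary and secondary analyses". Those methods are:

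- For 4SC (SAP Section 6.1.1): "Covariates for this analysis include the time to climb 4 stairs at baseline, treatment, visit and treatment by visit interaction".
- For the other endpoints (SAP Section 6.2): "The baseline stratification factor will be included in the model along with the other effects described in" Section 6.1.1.

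Age enters a planned model only for the thigh MRI analyses. For the muscle volume endpoints, "baseline age may be included as an additional covariate, if needed, to account for growth"; in the MRI-to-4SC regressions it is a covariate to be explored. SAP Section 5.2 lists age and steroid usage only as possible data-exploration covariates.

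On timing, Protocol Section 3.1 places the primary analysis after the last enrolled subject completes 49 weeks: "At that time, a limited number of study team members will be unblinded to the treatment assignments".

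**The concern.** In Period 1, randomisation balances age, steroid regimen and everything else in expectation, so a model with only the baseline value is adequate. In S6 nothing is randomised: every treated boy comes from the trial and every control from an external dataset. The same model then has to carry the whole burden of comparability, and it omits two variables that the SAP itself considers important enough to filter on.

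A filter guarantees only that both groups lie between the same limits. One group can sit near the bottom of the age interval and the other near the top. The protocol's steroid requirement (inclusion criterion 5 and Section 5.10.1) sets a minimum duration and recent stability and allows three agents, so regimens can also differ among boys who all pass.

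Separately, if source and filter are still open when treatment codes become known to some of the team, the control set could be settled with trial outcomes in view. SAP Section 5.1 applies the primary type I error rate to secondary analyses, so S6 could be reported as a significant two-year benefit on this basis.

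**Working it through.** **1. The plan's own figure.** S6 has no sample size, SD or target effect. The only sizing is for Week 49 (Protocol Section 9.1): difference 2.5 s, SD 4.0 s, 80% power, two-sided 0.05, 2:1 allocation, one interim analysis, 96 completers.
- Without an interim, the placebo n is 1.5 × (1.960 + 0.842)² × 4.0² / 2.5² = 30.1, rounded up to 31. The total is 31 + 62 = 93.
- With gamma-family spending at 50% information, 80% power needs 95.1 (gamma = −1, efficacy boundary only) or 96.1 (gamma = −2, with non-binding futility).

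The 96 is therefore reproduced. It belongs to the randomised test and does not change. Only the SD is borrowed below.

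**2. Selection against adjustment for S6**

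| Variable | Filter (6.2.1) | S6 outcome model (6.2, 6.1.1) |
|---|---|---|
| Baseline 4SC | range | yes for 4SC; stratum for other endpoints |
| Endpoint's own baseline | not named | yes |
| Age | interval | no |
| Steroid regimen | protocol requirement | no |
| Data source | open | no |

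The age interval is not stated in Section 6.2.1. The trial enrols 6 to <16 years (10 years wide), while the natural-history figures in the SAP version history cover 6 to <10 (4 years wide).

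**3. What an age imbalance would do (illustration; inputs assumed).** No document gives an age slope. Assumptions:
- no drug effect; 35 Sequence 1 boys against 100 controls;
- both groups within 6 to <16 years, age SD 1.5, means 8.5 and 8.5 + gap before truncation;
- baseline 4SC = 4.5 + 0.4 × (age − 8.5) + noise (SD 1.5);
- two-year change = 4.3 + slope × (age − 8.5) + 0.5 × (baseline − 4.5) + noise (SD 4.0);
- 4,000 replicates, one-sided 0.025.

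| Slope (s/year of age) | Gap (years) | No age term: estimate (s), error | Age term: estimate (s), error |
|---|---|---|---|
| 0.5 | 0.5 | −0.19, 4.6% | 0.01, 2.5% |
| 0.5 | 1.0 | −0.39, 7.2% | 0.01, 2.6% |
| 1.0 | 0.5 | −0.37, 6.8% | −0.02, 2.6% |
| 1.0 | 1.0 | −0.75, 14.0% | 0.02, 2.5% |
| 1.5 | 0.5 | −0.56, 8.9% | 0.00, 2.6% |
| 1.5 | 1.0 | −1.16, 25.4% | 0.03, 2.1% |

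Adjusting for baseline 4SC absorbs only part of the age effect. The age term works fully here because the simulated relation is linear. Younger controls would bias the result against the drug.

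**4. More controls do not help.** For a fixed bias b, the false-positive probability is 1 − Φ(1.96 − b/SE), with SE = SD × √(1/35 + 1/n). At SD 4.0 and b = 0.545 s it is 8.2% with n = 35 and 11.2% with n = 200. Standard error shrinks; bias does not.

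**5. Timing.** Protocol Section 3.3 allows 30 months of enrolment. Period 2 lasts 48 weeks, about 11 months. When the last subject reaches Week 49, boys enrolled in the first 30 − 11 = 19 months have reached Week 97. That is 19/30 = 63% of subjects, assuming uniform enrolment and no dropout. Much of the S6 outcome data would exist at the unblinding.

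**The case against.** **Age and steroids are not ignored.** Both are named selection variables, and the version history calls the comparator matched. The closing reference to the protocol in Section 6.2.1 can also be read as covering the 4SC and age limits. This stands as a qualification. On that reading, however, the age interval is the 10-year eligibility range, which leaves more room for imbalance, and the section still describes filtering rather than matching.

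**The one-year spread proves nothing about source.** The version history reports mean one-year change "ranging from 0.9 to 1.99 seconds" in boys aged 6 to <10 with baseline 4SC of 2.5 to 12 s. A reader might infer that choice of source alone moves the control by 1.99 − 0.9 = 1.09 s, or 1.09/2.5 = 44% of the design effect. The documents do not support this:
- No per-source means, sample sizes or SDs are given.
- The expected range of four equal-sized sample means from one population is 2.06 × SD/√n. With SD 4.0 and an assumed 57 per source, that is already 1.09 s. With 30 or 100 it is 1.50 or 0.82 s.
- The spread is a one-year figure without the steroid filter, and 2.5 s is the Week 49 target, not an S6 target.

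This objection stands in full; the range is context only.

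**Weighting is not clearly better than regression.** With about 35 treated boys, propensity weighting costs precision, and choosing it over covariate adjustment is partly preference. This also stands. Fitting source as a fixed factor would not work either, because source is aliased with treatment.

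**The stakes are limited.** S6 is a secondary aim to characterise long-term effects in a Phase 2 trial. A reader might also take it to be the only Week 97 efficacy evidence. It is not: SAP Section 3.3.3 plans within-subject evaluation in all sequences, and Section 6.1.2 plots 4SC change by sequence at Week 97. S6 is the only planned external-control comparison.

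**Conclusion.** The concern holds in this form: a non-randomised comparison is analysed with a model built for randomised arms, without age or steroid regimen, against a control set whose sources and covariates are open and which has no lock date. It can therefore be confounded, and the controls could be chosen after part of the team knows the treatment codes.

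The documents do not establish the size or direction of the bias. The 0.19 to 1.16 s and 4.6% to 25.4% are conditional on the assumed slopes, age gaps, SD and control size. Nor do the documents show that outcome-informed selection would happen; they only fail to prevent it.

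A reader might infer that balance and a lock would let a difference be attributed to the drug. That is too strong: unmeasured differences and differences between trial and registry settings would remain. The change reduces confounding and does not remove it. The Week 49 primary test is untouched. The point should be corrected but does not threaten the trial's main conclusion.

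**What to change.** Amend SAP Sections 6.2 and 6.2.1:

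1. Add baseline age and steroid regimen to the S6 outcome model for 4SC, 6MWD, FVC and NSAA, and define how regimen is coded.
2. Name the natural-history sources and state the 4SC, age and steroid bounds.
3. Lock the control records before any team unblinding at Week 49.
4. Report covariate balance between Sequence 1 and the controls.
5. Show results by source as a sensitivity analysis; do not fit source as a factor.
6. Optionally, add propensity-score weighting or matching to Sequence 1 as a further sensitivity analysis.

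The cost is SAP wording, modest programming and a small loss of precision from the extra covariates. No change to trial conduct or to the Week 49 analysis is needed.

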### **6.3. Other Endpoint(s)**

*All exploratory endpoints, including the pharmacologic and health outcome endpoints, will be summarized by treatment group and period. Additional analyses may be performed to understand the relationship between these endpoints and treatment.*

Any population PK/PD analysis conducted will be reported separately.

Additionally, data permitting, relationships between PF-06252616 PK, GDF-8, imaging data (DXA, MRI), 4 stair climb, immunogenicity and any safety signals may be explored.

#### **6.3.1. PK Analyses**

##### **6.3.1.1. Concentrations Below the Limit of Quantification**

In all data presentations (except listings), concentrations below the limit of quantification (BLQ) will be set to zero. (In listings BLQ values will be reported as “<LLQ”, where LLQ will be replaced with the value for the lower limit of quantification.)

##### **6.3.1.2. Deviations, Missing Concentrations and Anomalous Values**

In summary tables and plots of the median values at each time point, statistics will be calculated having set concentrations to missing if 1 of the following cases is true:

1. A concentration has been collected as ND (ie not done) or NS (ie no sample).

2. A deviation in sampling time is of sufficient concern or a concentration has been flagged anomalous by the pharmacokineticist.

Note that summary statistics will not be presented at a particular time point if more than 50% of the data are missing.

### 6.3.1.3. Pharmacokinetic Parameters

#### 6.3.1.3.1. Derivation of PK Parameters

PK parameters for PF-06252616 will be determined from the serum concentration-time profiles as described in the following table. Actual PK sampling times will be used in the derivation of PK parameters. For subjects in Sequence 2, PK samples collected during placebo treatment in Period 2 will be used to estimate  $t_{1/2}$  following the last dose of active treatment in Period 1.

Parameter	Definition	Method of Determination
All Subjects – Weeks 13, 29, 45, 61, 77, 93 (Last dose for each dose escalation level, Periods 1 and 2)		
$C_2$	Serum concentration in the nominal 2-hour sample (end of infusion)	Observed directly from data
$C_{\text{trough}}$	Trough (predose) serum concentration	Observed directly from data
Subjects in Sequence 2 – Week 45 (last dose in Period 1)		
$t_{1/2}^a$	Terminal elimination half-life	$\text{Log}_e(2)/k_{el}$ , where $k_{el}$ is the terminal phase rate constant calculated by a linear regression of the log-linear concentration-time curve. Only those data points judged to describe the terminal log-linear decline will be used in the regression
Subjects with additional PK sampling – Weeks 1, 13, 17, 29, 33, 45 (First and last dose for each dose escalation level in Period 1)		
$C_{\text{max}}$	Maximum serum concentration	Observed directly from data
$T_{\text{max}}$	Time for $C_{\text{max}}$	Observed directly from data
$\text{AUC}_{\tau}$	Area under the serum concentration-time curve over the dosing interval $\tau$ , where $\tau = 672$ hours (4 weeks)	Linear/Log trapezoidal method
$C_{\text{av}}$	Average serum concentration over the dosing interval	$\text{AUC}_{\tau}/\tau$
Subjects with additional PK sampling – Weeks 13, 29, 45 (Last dose for each dose level in Period 1)		
CL	Clearance	Dose/ $\text{AUC}_{\tau}$
Subjects with additional PK sampling in Sequence 2 – Week 45 (last dose in Period 1)		
$V_{\text{ss}}^a$	Volume of distribution at steady state	CL * MRT, where MRT is the mean residence time.
a If data permit		

Unless otherwise noted, parameters marked “if data permit” will be reported only where a well-characterized terminal phase is observed, defined as at least 3 points with a goodness of fit statistic for the log-linear regression ( $r^2$ ) of  $\geq 0.9$ .

090177e1909dd632\Approved\Approved On: 25-Mar-2019 05:54 (GMT)

